While data on Maraviroc blood levels are available from other studies, our patients are different from those previously studied, and these first cases will be of great value in determining the levels of drug we can achieve in this population

The time points of obtaining drug levels will be as follows:

- Hour 0- Pre maraviroc administration
- Hour 1 \pm 10 minutes - After maraviroc administration
- Hour 2 \pm 10 minutes- After maraviroc administration
- Hour 4 \pm 10 minutes- After maraviroc administration
- Hour 6 \pm 10 minutes- After Maraviroc administration
- Hour 8 \pm 10 minutes- After maraviroc administration
- Hour 12 \pm 20 minutes- After Maraviroc administration

Plasma concentration-time data will be explored graphically and the AUC will be estimated by non-compartmental analysis with the software package WinNonlin (Version 6.2, Pharsight Corporation, Palo Alto, CA). Full maraviroc PK profile and trough concentration data will be analyzed using a PK model-based Bayesian approach (MW/Pharm, MediWare, Groningen, the Netherlands).

Pharmacodynamic analysis will be performed in the laboratory using standard techniques.

Pharmacodynamic assessments will occur on days 0 +/-3 days and one time on day 14 +/- 3 days after stem cell infusion. Results will be available in a timely fashion to correlate with pharmacokinetic test results.

Dose escalation criteria-

Dose escalation will take place if all the requirements listed below are met:

1. The AUC/12 hours of the initial 2/3 patients is below 100 ng/ml

2. No more than 0 of 3 or 1/6 patients on the first dose level experience a dose limiting toxicity by day 30, defined as either-
 - a. Non-engraftment by day 30. Engraftment is defined as the first of three consecutive measurements of ANC>500/mcL over 3 or more days.
 - b. Grade 4 liver abnormalities, unless clearly related to stem cell transplant and not to the study drug, including but not limited to grade 4-5 liver toxicity due to hepatic veno-occlusive disease, grade 4-5 organ toxicities related to expected infections following stem cell transplant and their sequelae, or grade 4-5 toxicities related to graft versus host disease.

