 - c. Other grade 4-5 toxicity , unless clearly related to stem cell transplant and not to study drug, including but not limited to veno-occlusive disease of the liver, acute graft versus host disease, autoimmune cytopenias, infectious complications due to stem cell transplant, or organ toxicities due to conditioning regimens.

BSA	Original Dose	Dose escalation	Value increment/dose
<0.22	40 mg bid	50 mg bid	+ 10 mg
0.2-0.43	100 mg bid	120mg bid	+ 20 mg
0.44-0.72	200 mg bid	250 mg bid	+ 50 mg
0.73-1.19	300 mg bid	350 mg bid	+ 50 mg
1.20-1.30	300 mg bid	350 mg bid	+ 50 mg
1.31-1.73	300mg bid	350 mg bid	+ 50 mg
>1.73	300 mg bid	350 mg bid	+ 50 mg

Table 4. Table showing doses and increments for dose escalation of Maraviroc.

Stopping Rules

1. If the incidence of Grade 2-4 acute GI or Liver (visceral) graft versus host disease is greater than 50% in the first 20 subjects by day +100, the study will be stopped. Enrollment will not stop while the analysis is being conducted.

2. If 3 out of 6 subjects experience DLT by day +30 as defined above at the initial dose in the first phase (AUC analysis) of the study, the study will be stopped. Enrollment will not be suspended while the analysis is being conducted.
3. The study will be halted for any grade 4 liver toxicity occurring within 30 days of study drug administration and without clear attributable alternative cause. Enrollment will be suspended while an analysis of the toxicity is being conducted. Enrollment will only restart with approval of the Medical Monitor, IRB and FDA. (Of note: any grade 3 liver toxicity (ALT > 5xULN or Total Bilirubin > 3xULN), regardless of cause, will lead to permanent discontinuation of Maraviroc for that specific patient, but enrollment will continue.)

Primary study end points

1. Feasibility
2. GVHD incidence by day +100 (all grades)
3. pK target >100ng/ml

Secondary Study end points

1. Overall survival by day +100
2. Graft failure by day + 100
3. Primary disease relapse by day +100
4. Incidence of toxicities either due to drug or transplant
5. Infectious complications which include asymptomatic viremias for EBV, Adenovirus, CMV, and/or viral disease, bacterial and fungal infections as documented by blood cultures.
6. Time to neutrophil and platelet engraftment

GVHD will be graded according to IBMTR criteria as shown in table 5 [33]-

	Stage 0	Stage 1	Stage 2	Stage 3	Stage 4

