Study calendar for blood draws for patients undergoing formal AUC analysis-

Days	AUC	Trough drug level	Pharmacodynamic assessment
Pretransplant			x
Day 0	X (± 3 days)		X (± 3 days)
Day 7		x (± 2 days)	
Day 10	X (± 3 days)		
Day 14		x (± 3 days)	X (± 3 days)
Day 21		x (± 3 days)	

Table 6. Study calendar for blood draws for patients undergoing formal AUC analysis

For patients enrolled after maraviroc dose has been verified, the schedule for lab draws is shown on Table 7.

Days	Trough drug level	Pharmacodynamic assessment
Pretransplant		x
Day 0	x (± 3 days)	X (± 3 days)
Day 7	x (± 2 days)	
Day 14	x (± 3 days)	X (± 3 days)
Day 21	x (± 3 days)	

Table 7- Study calendar for blood draws for patients on second phase of study (after PK study complete and dose verified)

Volume of Blood Draws-

For pharmacokinetic analysis, we will need approximately 3 ml of blood, to be collected in an EDTA tube. Real time data results will be available to allow for dosing changes to

be made after the first 3 patients. For pharmacodynamics analysis, we will need 2 ml blood in a sodium heparin tube.

Discontinuation of therapy-

Since most patients experience severe toxicities while undergoing an allogeneic SCT, it will be the investigator's responsibility to determine whether certain adverse events are related to the study drug or not based on previous studies using the agent and the current labeling. Common Terminology Criteria for Adverse Events (CTCAE) version 4.0 will be used to report toxicities.

The following events will mandate stopping Maraviroc for a specific patient;

- Grade 3 liver toxicity (ALT > 5xULN or Total Bilirubin > 3xULN) regardless of cause

Maraviroc will not be restarted in these cases.

The following events will mandate holding Maraviroc therapy on a specific patient:

1. Grade 3 or higher toxicity (exclusive of liver toxicity, see section above), not attributable to underlying disease.
2. Infection, which requires treatment with a strong CYP450 inducer or inhibitor (predicted to adversely interact with Maraviroc) such as rifampin.
3. Drop in renal function to creatinine clearance <40 ml/min as measured by GFR or cystatin C.

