The drug can be restarted at the same dose after full recovery from the AEs. Maraviroc will be discontinued if the AE recurs after re-challenge. Any grade 3 liver toxicity (ALT > 5xULN or Total Bilirubin > 3xULN) regardless of cause will lead to permanent discontinuation of Maraviroc for that patient. The study will be halted for any grade 4 liver toxicity occurring within 30 days of study drug administration without clear attributable alternative cause (see stopping rules for details). Re-challenge is not permissible in the event of Grade 3 or higher liver toxicity (ALT > 5xULN or Total Bilirubin > 3xULN) regardless of cause. Any grade 1 or 2 toxicities related to study drug will not require study drug to be held.

Early termination of study drug-

Treatment will continue unless one of the following criteria applies:

1. A dose limiting toxicity (DLT) occurs. A DLT is defined as either-
 - a.) Non-engraftment by day 30, if assessed by the investigator to be related to the study drug. Engraftment is defined as the first of three consecutive measurements of ANC>500/mcL over 3 or more days.
 - b.) Grade 4 liver abnormalities, once other causes for liver toxicity have been ruled out.
 - c.) Other grade 4-5 toxicity determined by the investigator to be related with high probability to the study drug.
2. Any grade 3 or higher liver toxicity (ALT> 5xULN or Total Bilirubin > 3xULN) regardless of cause:
 - a. Any grade 3 liver toxicity (as defined above) will lead to permanent discontinuation of Maraviroc for that patient.
 - b. The study will be halted for any grade 4 liver toxicity occurring within 30 days of study drug administration without clear attributable alternative cause. (See stopping rules for specific details.)
3. Patient decides to withdraw from the study due to inability to take the drug.
4. Poor compliance to drug (missing either 6 consecutive doses (3 days) or 12 intermittent doses in the entire administration period (< 80% compliance)).

Patients removed from study for unacceptable adverse events will be followed until the adverse event resolves or stabilizes.

Toxicity Monitoring-

Maraviroc is generally well tolerated in children as noted in the phase 1 congenital HIV trial. However, a black box warning for hepatotoxicity exists. Therefore, liver function tests will be monitored on patients while on maraviroc every 48 hours until day+30 (+ 7 days).

General concomitant medication and supportive care guidelines

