Maraviroc is not known to significantly affect any metabolic pathway. However, inhibitors and inducers of the cytochrome P450 metabolic pathway affect its drug level. Generally, patients in this trial will receive prophylactic antifungals as directed by their attending physician, which may include either micafungin or ambisome. Other concomitant medications are allowed except for strong inducers or inhibitors of the cytochrome P450, such as voriconazole, phenytoin, carbamazepine and rifampin. (See table 2).

Should there be emesis within 30 minutes of taking maraviroc, the drug should be re – administered. However, any emesis after 30 minutes of taking maraviroc will not require the drug to be readministered.

Risk to unborn fetus-

It is recommended that patients on study utilize appropriate methods of contraception to prevent getting pregnant or fathering a child as the effects of maraviroc on the unborn fetus is unknown. All female patients routinely undergo a pregnancy test as part of pre bone marrow transplant evaluation and only proceed with transplant when it is confirmed that they are not pregnant. Therefore we will not repeat this test prior to starting maraviroc.

Risk associated with blood draws-

This study will require research blood to be drawn as specified time points as shown in the study calendar. This blood will be drawn from a central line whenever possible and will be combined with routine clinical blood draws whenever possible and will not exceed maximum allowed blood volume for that patient per day per standard of care.

Statistical analysis

The primary objectives of this phase I/II clinical trial are to establish a therapeutic dose of Maraviroc and test the 100 day incidence rate of any GVHD in pediatric patients undergoing allogeneic stem cell transplantation against a historical incidence rate.

Phase I will consist of the determination of a therapeutic dose. A dose escalation procedure outlined in the study design will be conducted until a dose which yields 2 of 3 patients with AUC > 100ng/ml and no drug related toxicities.

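### The 3-of-6 DLT stopping rule is worded for the initial dose and does not reach the planned escalated dose; the phase I acceptance wording should be aligned with the DLT limit

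*Combined protocol and SAP*

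**What the plan says.** All references are to the combined protocol and SAP.

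- **Dose escalation criteria.** Escalation needs low exposure ("The AUC/12 hours of the initial 2/3 patients is below 100 ng/ml") and acceptable safety ("No more than 0 of 3 or 1/6 patients on the first dose level experience a dose limiting toxicity by day 30"). A DLT is non-engraftment by day 30, a grade 4 liver abnormality, or another grade 4-5 toxicity. The liver and other-toxicity components exclude events clearly due to the transplant.
- **Table 4** ("Table showing doses and increments for dose escalation of Maraviroc") gives one higher dose for every body-surface-area band.
- **Stopping Rules, rule 2**: "If 3 out of 6 subjects experience DLT by day +30 as defined above at the initial dose" in the first phase, the study stops. Enrollment continues during the analysis.
- **Stopping Rules, rule 3**: "The study will be halted for any grade 4 liver toxicity occurring within 30 days of study drug administration" when no other cause is clear. It names no dose level.
- **Statistical analysis.** Escalation is "conducted until a dose which yields 2 of 3 patients with AUC > 100ng/ml and no drug related toxicities". No grade or tolerated number is given.
- **Discontinuation of therapy.** An individual's drug is held for "Grade 3 or higher toxicity (exclusive of liver toxicity, see section above), not attributable to underlying disease", and afterwards "The drug can be restarted at the same dose after full recovery from the AEs". Drug-related grade 1-2 events do not require a hold.
- **Study design.** The first part is restricted to ages 2-12 and runs until there are 12 dose verifications. The PK look after three patients leads either to continued observation or to escalation.

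**The concern.** A DLT-count stop guards against going on treating new patients at a dose that is already causing serious harm. That matters most at the highest dose used. Here the count rule is written for the lower of the two planned doses. If exposure is low and the dose is raised, the first recipients of the higher dose are children aged 2-12, and the readable text contains no DLT count at which dosing at that level stops. The events left uncovered are non-engraftment and non-liver grade 4-5 toxicity.

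A smaller point goes with this. The Statistical analysis section and the Dose escalation criteria describe tolerable toxicity in different terms. The investigator should not have to choose between them when declaring a dose established, because the established dose also helps decide which phase I patients enter the efficacy analysis.

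**Working it through.** The plan states no operating characteristic for these rules, so there is no figure to reproduce. The check compares the wording first and then sizes the gap.

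**Step 1. Which safeguards reach the escalated dose?**

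| Safeguard | Applies at the escalated dose? | Stops the dose level on a count of non-liver DLTs? |
|---|---|---|
| Escalation limit, 0/3 or 1/6 DLTs | No: first dose level | No |
| Stopping rule 2, 3/6 DLTs | No: initial dose | Only at the initial dose |
| Stopping rule 3, grade 4 liver | Yes | No: liver only |
| Stopping rule 1, visceral GVHD above 50% in the first 20 | Yes | No: GVHD only |
| Patient-level holds and discontinuation | Yes | No: one patient at a time |
| Medical monitor | Yes | No stated DLT threshold |

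The last column contains no rule that operates at the escalated dose.

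**Step 2. How often would the missing rule have been met?** Let r be the true non-liver DLT rate at the escalated dose. Unexplained grade 4 liver events are left out because one already halts the study. Assume six patients at that dose; the readable text does not fix the number.

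P(3 or more of 6) = 1 − [(1−r)^6 + 6r(1−r)^5 + 15r²(1−r)^4]

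- r = 0.10: 1 − (0.5314 + 0.3543 + 0.0984) = 0.016
- r = 0.20: 1 − (0.2621 + 0.3932 + 0.2458) = 0.099
- r = 0.30: 1 − (0.1176 + 0.3025 + 0.3241) = 0.256
- r = 0.40: 1 − (0.0467 + 0.1866 + 0.3110) = 0.456

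The documents give no value for r, so all four rates are assumptions.

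**Step 3. How likely is escalation at all?** Take criterion 1 as at least 2 of 3 patients below target, and let p be a patient's chance of a low AUC (also an assumption). P = 3p²(1−p) + p³, which is 0.028, 0.216 and 0.500 for p = 0.10, 0.30 and 0.50. Multiplying by step 2:

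- lowest pair: 0.028 × 0.016 = 0.0004
- p = 0.30, r = 0.30: 0.216 × 0.256 = 0.055
- highest pair: 0.500 × 0.456 = 0.228

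These are upper bounds for each pair, because escalation also needs the first-level DLT limit to be met.

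**Step 4. How large is the dose step?** Table 4 ratios are 50/40 = 1.25, 120/100 = 1.20, 250/200 = 1.25 and 350/300 = 1.17, so the increase is 17% to 25%.

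**Step 5. The acceptance wording.** Read literally, any drug-related event of any grade fails the Statistical analysis condition. For illustration, the pediatric HIV trial in the background section had treatment-related events in 14/78 = 17.9%, all mild to moderate. At that rate P(at least one in 3) = 1 − (64/78)³ = 0.45, with none of these events a DLT. On the narrowest reading, where toxicities means drug-related DLTs, the standards still differ at 1/6: the escalation limit tolerates it and the acceptance condition does not.

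**The case against.** The strongest reply is Figure 1. The Study design section routes the decisions through that graph, which could not be read here. Branches for an escalated cohort may sit there. This stands as a condition on the conclusion. Even so, rule 2's own words name the initial dose, so text and figure would need to agree.

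The DLT rates are also unsourced. The one pediatric safety record cited reported only mild-to-moderate treatment-related events, though in HIV patients rather than transplant recipients. The low end of the range therefore deserves equal weight, and at 10% the figure is 1.6%.

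A reader might infer more than the documents support:

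- **That the escalated dose has no safety cover.** It has several safeguards. A DLT attributed to the drug ends that patient's treatment (Early termination of study drug), so restarting after a hold is not the general response to a DLT. The monitor must review deaths and unanticipated serious events as they arise; six months is only the minimum schedule.
- **That phase I has no written end when PK is on target with 1/6 DLTs.** Study design ends the first part at 12 dose verifications and gives continued observation as the alternative to escalation.
- **That the acceptance wording changes the dose given.** Escalation is barred when AUC is on target, and Table 4 offers no lower level. The two passages also serve different decisions, and the statistical one defers to the study design, so it may be shorthand.

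Finally, rule 2 does not suspend enrollment while the analysis is done. Extending it adds a stop, not an automatic pause.

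**Conclusion.** The stopping-rule gap holds, subject to Figure 1. As worded, neither stopping rule 2 nor the escalation DLT limit covers the Table 4 dose, and the remaining safeguards do not supply a dose-level count of non-liver DLTs. Given escalation and six patients at that dose, the unguarded outcome has probability 1.6% to 46% across assumed DLT rates of 10% to 40%. Allowing for the chance of escalating, it is at most about 5.5% at p = r = 0.30, and 0.04% to 23% across the assumptions. The single modest dose step limits the consequence further. The gap still merits correction, because a stopping rule exists for unlikely but serious branches.

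The acceptance wording is a real inconsistency, but no changed dose or result has been shown to follow from it.

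**What to change.** 1. In stopping rule 2, replace the restriction to the initial dose with *at any dose level*, and make Figure 1 agree.
2. In the Statistical analysis section, replace the ungraded toxicity condition with the plan's own limit: *DLTs, as defined in the dose escalation criteria, in 0/3 or no more than 1/6 patients*. If zero DLTs is intended, say so in both places.

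Two matters are the sponsor's to decide: the dose to use if the escalated level proves too toxic, and the action at 2/6 DLTs. A mandatory return to the original dose is not proposed, since escalation would have happened because that dose missed the PK target.

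The cost is amendment wording and IRB approval, with no added patients, samples or visits.

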COVER PAGE FOR CLINICALTRIALS.GOV

Protocol Title: Maraviroc as graft versus host disease prophylaxis in pediatric and adult stem cell transplant recipients

NCT Number: NCT02167451

Document Version Date: 03/23/2018

Title of study: Maraviroc as graft versus host disease prophylaxis in pediatric and adult stem cell transplant recipients.

Principal Investigator: [name]

Co-Investigators: [name] [name], MRCP
[name], PhD
[name]
[name]
[name]
[name]
[name]
[name]
[name], PhD
[name]
[name], PhD
[name]
[name], DO, MPH

Statistician: [name]

Pharmacist: [name]

Abstract-

Acute graft versus host disease (GVHD) is the most significant complication of stem cell transplant (SCT), with high rates of morbidity and mortality. In children with GVHD, activated donor lymphocytes migrate to target organs and cause characteristic end organ damage to skin gut and liver. Small protein molecules called chemokines mediate the process of migration. CCR5, a chemokine receptor employed by the HIV virus to enter CD4 T cells, is also widely implicated in the pathogenesis of visceral GVHD, mediating migration of T-cells to target organs.

Maraviroc is an oral CCR5 antagonist that is currently FDA approved as antiretroviral therapy for HIV in adults. However, it has also been used to reduce visceral GVHD in murine models.

We hypothesize that addition of Maraviroc to our standard GVHD prophylactic regimen will reduce the incidence of acute visceral (gut and liver) GVHD in children at day + 100 after a stem cell transplant without impacting engraftment. Our initial study will investigate Maraviroc pharmacokinetics and pharmacodynamics to establish appropriate dosing for future studies. In the second stage of the study we will investigate efficacy. Patients will receive Maraviroc orally at the dose established in the first step of the study along with standard graft versus host disease prophylaxis from day -3 to day +30 after transplant, and will be observed until day + 100 for incidence of acute GVHD, infectious complications, relapse and overall survival. This study has high relevance as it may alter the rates of GVHD in children and improve overall survival after SCT.

Purpose of the Study

1. To establish the pharmacokinetics and feasibility of oral Maraviroc in children undergoing allogeneic stem cell transplantation (SCT).
2. To evaluate efficacy and adverse events of Maraviroc in prophylaxis of acute GVHD in children and young adults undergoing allogeneic SCT.

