In the phase 1 study, administration of the drug was briefly suspended in 7 of 13 patients because of grade 3 abnormalities on liver function testing (n=2) or grade 3 or 4 mucositis (n=5). Liver-function abnormalities did not recur when the drug was re-started. The adverse event profile was similar to the expected toxicity observed in patients undergoing reduced intensity conditioned SCT without maraviroc. In addition, there were no viral or fungal infections other than asymptomatic reactivation of cytomegalovirus. The incidence of bacterial infections was not higher than the expected rate for a reduced intensity transplant. In conclusion, Maraviroc was generally well tolerated in this study [30,31].

Research Plan

The study continues seamlessly from one stage to the next and therefore does not have “phases” in the conventional sense. The initial part of the study will be a dose finding and feasibility study. The second stage of the study will involve administering the appropriate dose of Maraviroc to children as a prophylactic agent against acute graft versus host disease. Maraviroc will be added to standard GVHD prophylaxis of a calcineurin inhibitor (cyclosporine or tacrolimus), methylprednisolone, mycophenolate mofetil (MMF) or methotrexate. The study plan is described below.

Number of Subjects

We plan to enroll 65 patients over the course of approximately 5 years.

Selection

This study will be conducted at Cincinnati Children’s Hospital, in patients 2 years of age-40 years of age who are undergoing allogeneic stem cell transplant.

Eligibility

Inclusion Criteria

1. Ages- 2 years and \leq 40 years. For Phase I, the dose finding part of the study, enrollment will be limited to ages 2-12 years as adult dosing is already available and it is likely that a teenager metabolizes the drug similar to adults.

2. All diagnoses are eligible
3. Stem cell source must be marrow, peripheral blood stem cells or cord blood from an unrelated or related donor
4. All conditioning regimens are eligible.
5. Patient must be planned to receive a calcineurin inhibitor (cyclosporine or tacrolimus) together with steroid, methotrexate or mycophenolate mofetil as GVHD prophylaxis.
6. Willingness and ability to provide signed informed consent (including assent, for ages 11-17 years)

Exclusion Criteria

1. Documented anaphylaxis to Maraviroc
2. Ex vivo T depleted grafts

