For the first part of the study, where full AUC analysis will be performed to verify the dose, we anticipate initially enrolling 12 patients to achieve 12 dose verifications. Any patients who do not achieve a complete PK data profile (i.e. due to suboptimal dose or incomplete course of study drug) will be replaced to achieve 12 dose verifications. The total number of patients will still remain 65 (Phase I and Phase II). The age of enrollment for these patients will be limited to 2-12 years old. This age restriction has been imposed because adult dosing for maraviroc in the stem cell transplant setting has already been established and it is likely that teenagers metabolize the drug similar to adults. The second part of the study, where full AUC analysis will not be conducted, will enroll the remaining patients between the ages 2-40 years.

We will enroll eligible patients and maraviroc will be administered as per study rules. Area under the concentration-time curve (AUC) determination will be performed on days 0 +/- 3 days and 10 +/- 3 days to account for weekends, national holidays or clinical deterioration not allowing for scheduled blood draws on the specified days. PK analysis will be performed after the first 3 patients. As per our study design graph, this is not an "interim" analysis, but an analysis to verify PK target attainment which then will drive either further observation or dose escalation. See Figure 1.

[figure not shown]

Figure 1. Study design

Pharmacokinetic measurement and analysis-

Blood for PK will be collected on day 0 +/- 3 days and Day 10 +/- 3 days. Complete PK profile (full AUC) will be performed on these days (see time points below). Evaluation of maraviroc trough levels will also be done routinely on all patients on study on days 0,7,14 and 21 in order to collect additional PK data, verify compliance and allow for additional dose corrections if necessary.

Target AUC/12 hours= $\geq 100\text{ng/mL}$ (based on HIV data)

PK processing will be performed at University of North Carolina's Clinical Pharmacology and Analytical Chemistry Laboratory using mass spectrometer with HPLC separation.

Plasma Maraviroc concentration data will be analyzed by compartmental and non-compartmental analysis with the help of [name], Director of Pediatric Pharmacology Research Unit (PPRU) at CCHMC, and parameter estimates generated will include clearance, half-lives, and volume of distribution along with area under the curve (AUC).

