All patients in phase I treated at the established dose as well as patients treated at a lower dose yet achieve a therapeutic pharmacokinetic level will be included in further analysis. The historical incidence rate of GVHD in pediatric patients undergoing allogeneic stem cell transplantation with GVHD prophylaxis agent of a calcineurin inhibitor+ methylprednisolone is 16% (BMT 2012 data at CCHMC). Assuming the incidence rate for patients treated at the dose established in phase I is 6% then a sample size of evaluable 65 patients provides an 80% power of detecting a difference between this rate and the historical incidence rate. This sample size determination was computed using a two-sided binomial test.

The exact two-sided 95% confidence intervals for the day 100 incidence rate of grade GVHD will be reported. For time-to-event endpoints, e.g., overall survival and time to occurrence of GVHD, we will present Kaplan-Meier curves and corresponding survival p-values will be computed using log-rank tests. Demographic information such as age and race will be tabulated. Descriptive statistics, including means, standard deviations, and ranges for continuous parameters, as well as frequencies for categorical parameters, will be presented

Regulatory Issues-

The protocol and informed consent document for this study will be approved in writing by the Institutional Review Board (IRB) prior to any patient being registered on the study.

Changes to the protocol, as well as a change of study staff, must also be approved by the IRB. Records of the Institutional Review Board review and approval of all documents pertaining to this study must be kept on file by the investigator and are subject to FDA inspection at any time during the study.

Informed consent will be obtained prior to the treatment of participants.

This protocol will be performed under an investigator-initiated IND.

Study Monitoring and Auditing:

Monitoring and auditing procedures will be followed to ensure that the study is conducted, documented, and reported in accordance with the IRB approved protocol, all applicable federal regulations and guidelines, and applicable regulatory requirements of Cincinnati Children's Hospital Medical Center.

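### The 16% historical rate used as the null describes pediatric patients on one prophylaxis regimen, but the trial tests patients aged 2 to 40 on several regimens, and no analysis set reconciles the two

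*Combined protocol and SAP*

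**What the plan says.** The Statistical analysis section sets the efficacy objective as to "test the 100 day incidence rate of any GVHD in pediatric patients undergoing allogeneic stem cell transplantation against a historical incidence rate". It then gives the benchmark for pediatric allogeneic transplant patients "with GVHD prophylaxis agent of a calcineurin inhibitor+ methylprednisolone is 16% (BMT 2012 data at CCHMC"). No count of patients or events stands behind the figure. The planned treated rate is 6%, and "a sample size of evaluable 65 patients" is said to give 80% power by a two-sided binomial test.

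The population is described more widely elsewhere:

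- Purpose of the Study: "To evaluate efficacy and adverse events of Maraviroc in prophylaxis of acute GVHD in children and young adults undergoing allogeneic SCT".
- Inclusion Criteria: "Patient must be planned to receive a calcineurin inhibitor (cyclosporine or tacrolimus) together with steroid, methotrexate or mycophenolate mofetil as GVHD prophylaxis".
- Research Plan: "Maraviroc will be added to standard GVHD prophylaxis of a calcineurin inhibitor (cyclosporine or tacrolimus), methylprednisolone, mycophenolate mofetil (MMF) or methotrexate".
- Study design: the 12 dose-verification places are limited to ages 2 to 12, and the second part "will enroll the remaining patients between the ages 2-40 years".
- Number of Subjects: "We plan to enroll 65 patients over the course of approximately 5 years".

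Primary study end points counts GVHD of all grades by day +100. The Statistical analysis section has one rule on who enters the analysis. It admits phase I patients treated at the established dose, or at a lower dose with a therapeutic drug level, and does not mention age or prophylaxis. The word evaluable is not defined.

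**The concern.** In a single-arm test the null rate takes the place of the control group, so it has to be the rate these patients would have had without the drug. Here it belongs to a narrower group, defined by age, by prophylaxis regimen and by one calendar year at one centre. This is the only efficacy comparison in the plan with a stated comparator, because the log-rank tests in the same section name none. If the no-drug rate in the enrolled mix is not 16%, the binomial test attributes the gap to maraviroc. A lower background can look like benefit. A higher one can hide a benefit or look like harm.

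**Working it through.** **1. Compare the populations.**

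| | Benchmark (16%) | Patients tested |
|---|---|---|
| Age | pediatric, no cut-off given | 2 to 40 years |
| Partner to the calcineurin inhibitor | methylprednisolone | steroid, methotrexate or mycophenolate mofetil |
| Source | one centre, 2012 | the same centre, about 5 years of accrual |
| Number | not stated | 65 |

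Only the 12 dose-verification places carry the age limit, so up to 65 − 12 = 53 places are open to age 40. That is a ceiling set by eligibility, not an expected number of adults. The objective says pediatric, but a pediatric analysis set would have fewer than 65 patients as soon as one adult enrolled, and the regimen difference would remain. The significance section says that methotrexate may be replaced by steroids or mycophenolate mofetil in small children, so regimen and age are likely to move together.

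**2. Reproduce the plan's own figure.** Inputs from the Statistical analysis section: n = 65, null 0.16, treated rate 0.06, two-sided. Alpha is not stated; I take 5% from the planned 95% interval. With X binomial:

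- Lower limit: P(X ≤ 4 | 0.16) = 0.0153 and P(X ≤ 5 | 0.16) = 0.0401, so benefit is declared at 4 or fewer events.
- Upper limit: P(X ≥ 17 | 0.16) = 0.0246 and P(X ≥ 16 | 0.16) = 0.0478, so harm is declared at 17 or more.
- Check against the exact 95% interval: 4/65 gives 1.7% to 15.0% and 17/65 gives 16.0% (0.1603) to 38.5%, so both exclude 16%. 5/65 gives 2.5% to 17.0% and does not.
- Power: P(X ≤ 4 | 0.06) = 0.649.

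The stated 80% reproduces only with the limit at 5 or fewer events, P(X ≤ 5 | 0.06) = 0.806, which is a 5% one-sided test. That is a separate matter. The two-sided 5% limits are used below.

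**3. Sensitivity to the background.** The documents give no no-drug rate for the enrolled mix. Let q be that rate; the values 12% and 20% are assumptions on either side of 16%. For an inert drug:

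| q | False benefit, P(X ≤ 4 given q) | False harm, P(X ≥ 17 given q) |
|---|---|---|
| 12% | 9.7% | 0.1% |
| 16% | 1.5% | 2.5% |
| 20% | 0.2% | 14.0% |

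**4. Power depends on what is held constant.** If the treated rate stays at the planned 6%, power against the fixed 16% is P(X ≤ 4 | 0.06) = 65% whatever q is. If one assumes instead a constant relative reduction of (16 − 6)/16 = 62.5%, the treated rate at q = 20% is 0.375 × 20% = 7.5%, and power is P(X ≤ 4 | 0.075) = 46%. The plan does not state a constant relative reduction.

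**5. Sampling error of the benchmark.** For assumed denominators of 50, 100 and 150, a 16% rate (8/50, 16/100, 24/150) has exact 95% intervals of 7% to 29%, 9% to 25% and 11% to 23%. The test treats 16% as known.

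**The case against.** A fixed historical rate is an ordinary choice for a small single-arm phase I/II trial, and the benchmark comes from the same hospital. The objective says pediatric patients. Prophylaxis, graft and donor details are collected and age is tabulated, so a reader could at least see how the mix departs from the benchmark. All of this is fair, but none of it changes the test. No set applies the pediatric wording, and collecting a variable does not adjust for it.

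Four stronger readings are tempting and are not supported:

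- A reader might infer that the true background is much higher, because the significance section quotes 31.9% and 44.4% for calcineurin inhibitor plus methotrexate. Those rates are for grade II-IV disease in a randomized matched related donor trial. They come from a different population and a narrower endpoint, and cannot serve as a null here.
- A reader might infer that the plan's power collapses. Step 4 shows that this needs a constant relative effect, whereas the plan fixes an absolute 6%.
- A reader might infer that the 16% uses another grade or time window. The sentence giving it states neither, but the objective read with it makes any grade by day 100 the natural meaning. What is plainly missing is the numerator and denominator.
- A reader might infer that the null should be re-weighted to the enrolled mix and used in the primary test. That rate would not be known until accrual ended and would be treated as exact although estimated. It fits better as a sensitivity analysis.

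One reservation stands against any repair. Eligibility also admits all diagnoses, all conditioning regimens, related and unrelated donors and three stem cell sources, so matching on age and regimen leaves other confounding.

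**Conclusion.** The concern holds. The null is defined for a narrower population than the one tested, and nothing in the plan restricts, stratifies or adjusts the comparison. A result that differs from 16% cannot be attributed to the drug without assuming that regimen and age make no difference. The direction and size of any bias are unknown. The figures of 9.7% false benefit at a 12% background and 14% false harm at 20% show sensitivity under assumed backgrounds and an assumed two-sided 5% level; they do not demonstrate a bias. This should be corrected, with medium confidence about its practical weight, because the enrolled mix is not stated.

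**What to change.** Before any analysis of the primary endpoint:

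1. Recompute the historical rate of any-grade GVHD by day +100, graded by Table 5, from the same centre's past patients who meet this protocol's age and prophylaxis criteria. Fix the source patients in writing and state the numerator and denominator. Use that rate as the null and restate the power.
2. If too few past methotrexate, mycophenolate mofetil or adult patients exist, keep 16% and limit the claim against it to the patients who match it (pediatric, calcineurin inhibitor plus steroid), with the reduced power stated.
3. As sensitivity analyses, report (a) the test in that matched subset; (b) a comparison with a benchmark standardised to the enrolled regimen and age mix, and donor type where cells allow; (c) the difference from the benchmark with a 95% interval that includes the benchmark's sampling error.
4. Show day-100 rates by regimen and age group.

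The cost is a retrospective data pull and a paragraph of text, with no new patients or procedures. The restated power may be less favourable. With exact two-sided 5% limits, 65 patients and a treated rate of 6%, a null of 12% gives P(X ≤ 2 | 0.06) = 24%, and a null of 20% gives P(X ≤ 6 | 0.06) = 91%. In a matched subset tested at 16% against 6%, power is 42% with 50 patients, 30% with 40 and 16% with 30. With 20, even zero events would not reach the limit, since 0.84^20 = 0.031 exceeds 0.025. Confounding by donor, graft and conditioning would remain and should be acknowledged.
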